**Name of the Study:**

**Randomized Control Trial (RCT):  
Superiority Study for Inter-scalene Block  
Execution Time in Traumatological  
Shoulder Surgery and Non-inferiority for  
Effectiveness between Two Blocking  
Methods: Catheter Over Needle (CON) vs  
Catheter Through Needle (CTN).**

**NCT: Not Assigned yet**

**Date of last review board: 21/09/2022**

Protocol This clinical trial will be registered on [www.clinicaltrials.gov](http://www.clinicaltrials.gov). Upon approval from the institutional ethics review committee, the recruitment of 36 patients per group undergoing rotator cuff or proximal humerus surgery, who meet the inclusion criteria, do not have exclusion criteria, and agree to participate in the study, will be conducted. Informed consent will be obtained, and prior randomization generated by a computer program, each patient will be assigned to the allocated group: Catheter Through Needle (CTN) or Catheter Over Needle (CON). The inclusion criteria will be: age over 18 years, ASA I-III, BMI 18-35 kg/m^2. Exclusion criteria will be inability to consent to the study, coagulopathy, sepsis, renal or hepatic failure, allergy to local anesthetics, previous peripheral nerve damage, and refusal of the postoperative continuous block technique. Block execution: After the patients arrive at the operating room, an 18 or 20-gauge intravenous Teflon catheter will be placed in the contralateral arm to the operated limb, installed in the preoperative unit by the responsible nurse. Monitors will be set up: continuous 3-lead electrocardiography, non-invasive ankle pressure, and pulse oximetry. After the safety pause, the patient will be premedicated with midazolam 1-4 mg and fentanyl 50-100 mcg. Supplementary oxygen will be administered via a Venturi mask at 4 L/min. With the patient in supine and semisitting position, an ultrasound-guided inter-scalene block image will be obtained (according to the established model for an acceptable injection site) ipsilateral to the surgery, using a linear ultrasound transducer of 6-13 MHz (Sonosite). Then, the area will be aseptically prepared with chlorhexidine, and local anesthesia will be administered with 2% lidocaine, 3-4 ml. Using a plane technique, the Contiplex® C needle set will be used for the CON randomized group, and the Contiplex Touhy™ (CT) set for the CTN group. The time in seconds from the start of the puncture with both catheters until the application of 3M™ Tegaderm™ dressing for fixation will be timed. All blocks will be performed by non-expert residents trained in the use of each needle-catheter set and/or by an expert anesthesiologist (in equal proportion in each group). The number of attempts or punctures will also be measured, defining each attempt as any reinsertion of the needle through the skin once the block has started. After completing the block, the patient will be anesthetized with balanced general anesthesia, using Propofol 1-2 mg/kg as an induction agent, fentanyl 3-5 mcg/kg, neuromuscular relaxation as needed. The airway will be instrumented with a laryngeal mask or endotracheal tube at the anesthesiologist's discretion. Ketorolac and paracetamol will be used as multimodal analgesia unless contraindicated. Dexamethasone IV and/or ondansetron will be used for the prevention of nausea based on classic criteria for preventing postoperative nausea and vomiting. Once the surgery is finished, a home analgesia pump (elastomeric pump) will be connected to the catheter, and the patient will be educated on the outpatient removal of the catheter according to the institutional protocol. Telephone follow-up will be conducted to assess pain, complications, the need for urgent oral analgesia, or accidental catheter removal, filling out the attached form in the annex. Effective block will be classified as pain on the visual analog scale (VAS) equal to or less than 4 out of 10, and accidental removal as displacement of more than 2 cm from the fixation point recorded on the anesthesia sheet. The installation times and effectiveness of both catheter sets will be compared at 24- 48-72 hours.

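### The protocol promises the same resident/expert mix in both groups, but the allocation it describes has no step that secures it

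*Protocol*

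**What the plan says.** The title makes execution time the superiority question ("Superiority Study for Inter-scalene Block" execution time). The unnumbered protocol text defines the measurement: "The time in seconds from the start of the puncture with both catheters until the application of" the fixation dressing.

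On who performs the block, the same text names trained non-expert residents "and/or by an expert anesthesiologist (in equal proportion in each group"). It gives no rule for which operator takes which patient.

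On allocation, there is one clause, which covers both CTN and CON: "prior randomization generated by a computer program, each patient will be assigned to the allocated group". On size, it plans "the recruitment of 36 patients per group undergoing rotator cuff or proximal humerus surgery", so 72 blocks in all. No strata, block sizes or minimisation factors are named.

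The groups use different needle sets (the Contiplex C "needle set will be used for the CON randomized group, and the Contiplex Touhy" set for CTN), so whoever performs the block sees the group.

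**The concern.** Equal operator mix is stated as a feature of the design, but the allocation described contains no step that produces it. Two routes to equality remain. One is chance. The other is picking the operator after the group is known, so as to even up the counts. The text does not say which is meant.

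Execution time records the operator's own performance and plausibly depends on experience. Under the first route the promise often fails, and the comparison loses precision. Under the second the counts can be made equal, but the person choosing the operator knows the group and may also know the patient. Equal counts do not rule out that different kinds of patient reach the experts in each group.

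An SAP can adjust for operator class. It cannot create the balance at allocation, and it cannot move the choice of operator to before allocation.

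**Working it through.** **Inputs.** From the protocol: 36 per group, 72 blocks, computer randomisation, no stated operator stratum. The protocol gives no expert share, no SD and no effect size, so every other input below is an assumption. The 36 per group cannot be reproduced, because no error rate, power or effect is stated; the point does not depend on it.

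**1. Chance balance without a stratum.** Let K of the 72 blocks be done by experts, with the operator fixed independently of group. The number x of expert blocks in one group of 36 is hypergeometric:

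P(x) = C(K, x) · C(72 − K, 36 − x) / C(72, 36)

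The gap in expert share between groups is |2x − K| / 36. The match is exact when x = K/2.

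| Assumed K (share) | P(exact match) | P(gap ≥ 6/36, i.e. 17 points) | SD of gap |
|---|---|---|---|
| 18 (25%) | 0.214 | 0.173 | 10.3 points |
| 24 (33%) | 0.197 | 0.211 | 11.2 points |
| 36 (50%) | 0.186 | 0.238 | 11.9 points |

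The parenthesis in the protocol could mean the same mix in both groups, or half and half within each group. The second implies the first, so neither is secured.

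**2. The same mix with a stratified list.** Lists were simulated within operator class, in permuted blocks of 4 or 6 chosen at random, for K = 18, 24 and 36. The match was exact in about 60% of lists. With these even strata the gap never exceeded 5.6 points; with odd strata (19, 25 or 35 experts) the maximum was 8.3 points. Group sizes departed from 36 each in about 37% to 39% of lists. The difference between groups averaged 0.8 patients and was at most 4.

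**3. What an ignored operator effect costs in power.** Assumptions: a true effect of 0.67 SD (SD within operator class), two-sided 5%, a 50:50 mix, and a resident-expert gap of D SD. The variance with operator class ignored is V = 1 + D² × 0.5 × 0.5. The signal is 0.67 × √18 = 2.843.

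- Mix forced equal, class ignored: power = Φ(2.843 − 1.96 × √V)
- Mix left to chance, class ignored: power = Φ(2.843 / √V − 1.96)

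| D | V | Forced, ignored | Chance, ignored |
|---|---|---|---|
| 0 | 1 | 81% | 81% |
| 0.5 | 1.0625 | 79% | 79% |
| 1 | 1.25 | 74% | 72% |
| 1.5 | 1.5625 | 65% | 62% |

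With operator class as a factor, simulated power at D = 1 and 1.5 was 79% to 80%, whether or not the mix was forced equal. The power is therefore recovered by the factor and not by the stratum. When the mix is forced equal and class is ignored, the type I error is 2.8% at D = 1 and 1.4% at D = 1.5. The test is then conservative.

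**The case against.** The strongest reply is that nothing here is false or contradictory. The protocol sets a constraint on operator mix and leaves out the mechanism. Its single clause on allocation is equally silent on blocks, strata and concealment, so silence on an operator stratum does not show that there is none. List details are often kept in an SAP or randomisation plan. This stands in part: the list may already be stratified, and one added sentence may settle that half of the point. It does not settle when the operator is chosen, which is trial conduct that an SAP cannot repair.

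Second, simple randomisation balances operators in expectation. That is correct, and chance imbalance is not bias. But the protocol promises equal proportions, not equality on average.

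Third, the stratum buys almost no power, and at a resident-expert gap of 0.5 SD there is little to recover (79% against 81%). This also stands. The case for the stratum is that it delivers the stated mix.

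Fourth, the remedy does not guarantee exact equality either. True, but it replaces gaps that reach 17 points in about a fifth of trials with gaps of at most 5.6 points when strata are even.

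A reader might go further and infer that operators are assigned by case difficulty, or that the time comparison is biased towards one set. The document does not support this. It describes no such practice, and any error rate for it would rest entirely on invented figures for case difficulty and steering, so none is given here. Nor does ignoring operator class under a forced equal mix create false superiority; it makes the test conservative.

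**Conclusion.** The point holds as a gap between a stated commitment and the means described to meet it. It is not evidence of an unequal mix or of bias. Without an operator stratum, and for an assumed expert share of 25% to 50%, the promised mix would be met exactly in about one trial in five. Meeting it instead by late choice of operator leaves a route to selection on an unblinded, operator-timed superiority endpoint.

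The loss of power depends on an unknown resident-expert gap: about 2 percentage points at 0.5 SD, 7 at 1 SD and 16 at 1.5 SD when the mix is equal and class is ignored. An analysis factor in the SAP would recover it. If one class performed every block, which the protocol's and/or wording would permit, the point would fall away. The correction should be made because it is cheap and because the timing of the operator choice cannot be put right at analysis. Confidence is medium, since an unstated stratified list remains possible.

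**What to change.** State in the protocol how the mix is kept equal:

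1. Name and record the operator class (resident or expert) for each patient before that patient's allocation is opened.
2. Stratify the computer list by operator class, in permuted blocks of varying size, concealed from those who enrol patients and those who perform blocks.
3. Include operator class as a factor when comparing execution times. This may sit in the SAP.

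If the list is already stratified by operator class, say so, and say that the operator is named before allocation. If recruitment has begun without this, record the operator before allocation from then on and adjust for operator class.

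The cost is a regenerated list, two or three sentences and a slightly earlier naming of the operator, with no extra patients or staff. There are two drawbacks. Groups may end up to 4 patients apart. Blocking also makes some allocations certain to someone who knows all earlier ones: about 33% with a known fixed block of 4 and 25% with a fixed block of 6, against 6% with the two sizes mixed at random. Because performers see the group, that is the reason for varying block sizes and for concealment.

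### Can accidental catheter removal, defined by a 2 cm threshold, be collected by telephone from patients at home?

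*Protocol*

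**What the plan says.** All the relevant text is in the Protocol's single unnumbered block under the review-board date.

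- **Definition.** The outcome is "accidental removal as displacement of more than 2 cm from the fixation point recorded on the anesthesia sheet". It is a centimetre threshold against a reference position noted when the catheter is placed.
- **Collection.** "Telephone follow-up will be conducted to assess pain, complications, the need for urgent oral analgesia, or accidental catheter removal", and the caller does this by "filling out the attached form in the annex". The annex is not shown.
- **Setting.** The patient goes home with a pump attached to the catheter. On instruction, the Protocol states only this: "the patient will be educated on the outpatient removal of the catheter according to the institutional protocol". That institutional protocol is not shown either.
- **Role of the outcome.** The study title names superiority for execution time and non-inferiority for effectiveness. Effectiveness rests on pain: "Effective block will be classified as pain on the visual analog scale (VAS) equal to or less than 4 out of 10". The closing sentence reads "The installation times and effectiveness of both catheter sets will be compared at 24- 48-72 hours" and does not list accidental removal.
- **Size.** The plan foresees "the recruitment of 36 patients per group".

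**The concern.** Of the items covered in the call, pain and urgent analgesia are things a patient can simply report. So is a catheter that has come out completely. A shift judged against 2 cm is different, because someone has to read a position. The text shown names no visit, examiner, photograph, depth mark or patient instruction for that reading, and the only teaching it describes concerns taking the catheter out.

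If nobody reads the position, the threshold is applied by impression. The likeliest error is that partial slips go unnoticed and the outcome drifts towards complete loss. Smaller slips could also be counted by mistake. If the error is equal in both arms, a true difference between the catheter sets on this outcome would look smaller than it is. In a trial of two catheter designs, that would be an unwelcome loss of information.

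**Working it through.** **Step 1: are the two rules incompatible?** Set side by side, they are:

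| Element | What the Protocol fixes |
|---|---|
| Reference position | Recorded on the anesthesia sheet |
| Threshold | More than 2 cm from that reference |
| Route | Telephone, with the annex form |
| How the current position is obtained | Not in the text shown; annex form and institutional protocol not shown |

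A caller holding the anesthesia sheet has the reference. The one missing element is the current position, which a patient or helper can be asked to describe. Supplying it leaves both the threshold and the telephone route as they are, so the rules do not contradict each other. The phrase about the anesthesia sheet could grammatically attach to the displacement rather than to the fixation point. That changes nothing here, because the sheet belongs to the operating-room stage and would not supply a later position under either reading.

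**Step 2: what could misreading do?** The Protocol states no displacement rate and no reading error, so there is no figure to reproduce. Everything below except the 36 per group is assumed.

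Inputs: p1 and p2 are the true rates in the two arms; s is the share of true displacements recorded; f is the share of the other patients wrongly counted. s and f are taken as equal in both arms.

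Observed rate = p·s + (1 − p)·f, so observed difference = (p1 − p2)·(s − f).

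| True rates | s | f | Observed rates | Observed difference |
|---|---|---|---|---|
| 25% vs 5% | 1 | 0 | 25% vs 5% | 20 points |
| 25% vs 5% | 0.75 | 0 | 18.75% vs 3.75% | 15 points |
| 25% vs 5% | 0.5 | 0 | 12.5% vs 2.5% | 10 points |
| 25% vs 5% | 0.5 | 0.05 | 16.25% vs 7.25% | 9 points |
| 25% vs 5% | 1 | 0.10 | 32.5% vs 14.5% | 18 points |
| 15% vs 5% | 0.5 | 0 | 7.5% vs 2.5% | 5 points |

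For the fourth row: 0.25 × 0.5 + 0.75 × 0.05 = 0.1625; 0.05 × 0.5 + 0.95 × 0.05 = 0.0725; difference 0.09.

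In patients, 25% and 5% of 36 are 9.0 and 1.8 expected events. At s = 0.5 and f = 0 they become 4.5 and 0.9.

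**Step 3: would better reading rescue a test?** The Protocol announces none for this outcome. If one were run with error-free reading (two-sided Fisher exact test at 0.05, 36 per arm), power would be about 57% for 25% vs 5% and about 15% for 15% vs 5%. At best, a cleaner reading sharpens a descriptive rate.

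**Step 4: do the title hypotheses use this outcome?** Execution time is clocked in the operating room, before any follow-up. Effectiveness is a pain score cut-off. Neither takes catheter displacement as an input.

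**The case for a change.** The strongest case for acting is that measurement, unlike analysis, cannot be repaired later: a position not read during follow-up is lost, and no statistical analysis plan can recreate it. Accidental removal is also one of only two outcomes the Protocol defines by a threshold, which suggests the authors care about it. The remedy would be cheap: a card at discharge and one standard question per call.

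Part of this stands. The text shown does not describe the reading, and equal error between arms is an assumption. The two sets differ by design, so a slip might be easier to see with one than with the other. With true rates of 25% in both arms and s = 1 in one arm but 0.5 in the other (f = 0), the observed rates would be 25% and 12.5%, a spurious gap of 12.5 points. The Protocol gives no ground for expecting such a gap. It describes one dressing and one follow-up procedure for both groups.

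The argument does not show that the plan fixes anything wrongly. A standard question on a call form is exactly what the cited annex exists to hold, and its absence from the material at hand is not evidence that it was omitted. The simpler alternative, counting only catheters that are fully out, would discard the partial displacement the authors chose to include. Choosing between a finer outcome that is harder to read and a coarser one that is easy to report is a fair trade-off, not an error to correct.

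**Conclusion.** No change to the plan. What the Protocol leaves open is an operating detail of data collection, naturally settled on the follow-up form, and its stated rules are compatible. The possible loss is confined to partial displacements, since a catheter that is fully out can be reported by telephone. In the illustrations with equal error in both arms, the true difference shrinks by between a tenth (20 to 18 points) and a little over a half (20 to 9 points). These figures rest wholly on assumed rates and errors and are not properties of this trial.

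The execution-time and effectiveness hypotheses are not directly affected. This conclusion assumes that the team completing the form asks about catheter position in the same way in both arms, which is ordinary good practice. If the form proved silent, adding that question would be a matter of form design and would leave the definition, the follow-up route and the planned comparisons as they are.

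### Does comparing effectiveness at 24, 48 and 72 hours, without one summary per patient, waste power that 36 patients per group could have given?

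*Protocol*

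**What the plan says.** The title promises "Non-inferiority for" effectiveness, next to superiority for execution time. The protocol text plans "the recruitment of 36 patients per group undergoing rotator cuff or proximal humerus surgery". It fixes the binary outcome: "Effective block will be classified as pain on the visual analog scale (VAS) equal to or less than 4 out of 10". The data come from calls to the patient: "Telephone follow-up will be conducted to assess pain, complications, the need for urgent oral analgesia, or accidental catheter removal". The closing sentence gives the times: "The installation times and effectiveness of both catheter sets will be compared at 24- 48-72 hours".

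The protocol gives no margin, significance level, power, expected rate or correlation between times. It names no main time and no summary over the three times. It also does not call for three separate tests, for success at all three times, or for success at any one of them.

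**The concern.** One yes/no outcome is seen three times in the same patients, and nothing in the protocol joins the three results. Read as three separate comparisons, every way of using them looks weak:

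- One time alone has limited power.
- Requiring all three times has less.
- Accepting any one of them inflates the risk of a false claim of non-inferiority.

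A per-patient share of the three assessments with VAS of 4 or less would use calls already planned and need no more patients. At an assumed 90% rate and 15-point margin, two equally good catheters would give an inconclusive result in about 4 of 10 trials at one time, against about 1 to 3 of 10 with the share. The closing sentence also attaches installation times to 24, 48 and 72 hours although they are measured once, so it looks loosely drafted in any case.

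**Working it through.** **Inputs.** From the protocol: 36 per group, the binary outcome, three times. Assumed: one-sided 2.5%, 80% power, equal true rates p in both arms and at all times, no missed calls, and the correlation between times. The figure of 36 cannot be reproduced, because the protocol gives no inputs for it.

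**One time.** SE = √(2p(1−p)/36), and the margin with 80% power is (1.96 + 0.84) × SE. At p = 0.90, SE = √(0.18/36) = 0.0707 and the margin is 2.80 × 0.0707 = 19.8 points. So 36 per group suits a margin of about 20 points at a 90% rate, and nothing shows that number to be wrong.

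**Share of three times.** With correlation φ between the yes/no results, the SE is multiplied by √((1 + 2φ)/3). A correlation of 0.5 can mean two things:

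- Yes/no results correlated 0.5: the factor is √(2/3) = 0.816 at every rate, an 18% reduction.
- An underlying (latent) normal variable correlated 0.5: φ is then only 0.20 to 0.32, and the reduction is about 26% to 31%.

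| Rate | One time | Share, latent 0.5 (φ) | Share, φ = 0.5 |
|---|---|---|---|
| 95% | 14.4 | 9.9 (0.20) | 11.8 |
| 90% | 19.8 | 14.0 (0.25) | 16.2 |
| 85% | 23.6 | 17.0 (0.28) | 19.3 |
| 80% | 26.4 | 19.2 (0.30) | 21.6 |
| 70% | 30.3 | 22.3 (0.32) | 24.7 |

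Both share columns are correct on their own scale. The range of 10 to 22 points therefore holds only for the latent correlation.

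**Power at 90% and 15 points.** Power = Φ(margin/SE − 1.96).

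- One time: Φ(0.15/0.0707 − 1.96) = Φ(0.16) = 56%.
- Share, φ = 0.25: SE = 0.0707 × 0.707 = 0.050, and Φ(3.00 − 1.96) = 85%.
- Share, φ = 0.5: SE = 0.0577, and Φ(2.60 − 1.96) = 74%.
- Share, φ = 1 (every failure lasts throughout): 56%, no gain.

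Simulation with a t interval gives 61% for one time and 89/84/73% for the share at latent 0.3/0.5/0.8.

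**Is it the same question?** Only the VAS threshold stays the same. A deficit of 15 points at 72 hours alone is an average deficit of 15/3 = 5 points over the three times, well inside a 15-point margin on the share. Simulated with 36 per arm and a 90% rate otherwise, such a catheter passes on the share in about 51%, 45% and 37% of trials at latent 0.3, 0.5 and 0.8. The 72-hour comparison passes it in about 3%. The same 15 points is thus a looser tolerance on the share than at one time, and the power gain at equal margins is not like for like.

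**Rules the protocol does not state.** Requiring all three times gives 27/29/36% power at 90% and 15 points. Accepting any one gives 5.5% to 8.8% false non-inferiority over the four cases simulated (rates 90% and 80%, margins 15 and 20 points). Both sets of figures describe decision rules that appear nowhere in the protocol.

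**Installation time.** The protocol text defines it as "The time in seconds from the start of the puncture with both catheters until the application of" the fixation dressing. It is one value per patient, so the closing sentence cannot lead to a different analysis of it.

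**The case for a change.** The strongest case for the concern is that the gain is real and costs no patients or calls. The quoted words are exact, the figures reproduce under their stated assumptions, and across plausible correlations the share needs a smaller margin for the same power. Its false non-inferiority rate stays at 2.2% to 2.9% in the four cases simulated. The drawback can be softened by still reporting each time with its own interval. And since the closing sentence is loosely worded about installation times, a summary could be added in the same edit.

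What stands is that a share over 72 hours is a legitimate option, and that the wording on installation times is a drafting slip. What does not stand is the step from an available option to a fault. A repeated-measures model, a named main time or a summary would each fit the closing sentence, and an analysis plan is the usual place to choose. A share would also need its own justified margin, so the change is larger than one sentence. Late or lasting failure is a plausible way for two catheters to differ: the protocol defines "accidental removal as displacement of more than 2 cm from the fixation point recorded on the anesthesia sheet". That is the setting in which the share gains least or hides most.

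**Conclusion.** The concern does not hold. The protocol states no rule for using the three times that could be wrong, and no figure that fails to reproduce. Leaving the combination of repeated assessments to the analysis plan is ordinary practice, and if that plan combines the times the point disappears altogether.

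The possible gain is a detectable margin of about 10 to 22 points (latent correlation 0.5) or 12 to 25 points (yes/no correlation 0.5) instead of 14 to 30. It falls to nothing if every failure lasts throughout. It is bought by replacing effectiveness at each time with average effectiveness over 72 hours, which makes a catheter 15 points worse at 72 hours far easier to pass: about 37% to 51% of trials against 3%. All of this rests on assumed rates, significance level, power and correlation. Only the 36 per group, the VAS threshold and the three times come from the protocol. Choosing between the two measures is a matter of preference. The slip on installation times changes no result.
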